## **5.3 Michigan Hand Questionnaire**

The MHQ is a validated, 63 question measure featuring 6 domains: overall hand function, activities of daily living, work performance, pain, aesthetics and patient satisfaction with hand function [3, 4]. Each item is scored between 1 and 5, with some items pertaining to a specific hand and some pertaining to both hands.

The MHQ can be used to generate 7 scale/summary scores for the left hand, right hand and for both hands, giving a total of 21 different summary scores as follows;

- 3x Overall Function scale scores
- 3x Activities of Daily Living scale scores
- 3x Work scale scores
- 3x Pain scale scores
- 3x Aesthetics scale scores
- 3x Satisfaction scale scores
- 3x Overall MHQ scores

Analysis of this data will be concerned with the 6 scale scores and overall MHQ score calculated for the reference hand. Participants complete the MHQ at baseline and 12 and 24 months post treatment. The scoring procedure for the MHQ is given in Appendix C.

#### **5.4 Single Assessment Numeric Evaluation**

SANE [5] is a single patient reported numerical assessment of hand function, provided by means of a visual analogue scale (VAS). Participants are asked the following question

*How would you rate your hand function today (with normal being 100%)?*

Participants respond by marking a single point on a line between 0 and 100%, to indicate the extent to which they perceive their hand function as being normal. A SANE score is collected at baseline, 2 and 6 weeks post treatment and 3, 6, 12 and 24 months post treatment.

#### **5.5 Overall hand assessment**

Participants are asked the following question at 3, 6, 12 and 24 months post treatment.

*Overall, how are the problems now, with the hand in which you had treatment, compared to before?*

Participants are given a choice of the following 7 responses; *Cured, Much better, A little better, The same, A little worse, Much worse, Terrible.*

#### **5.6 Joint measurements**

Goniometric measurements are collected and recorded by investigators in clinic. These will be used to assess range of movement (RoM) and recurrence of contracture post treatment. The collection of this data is summarised in Table 1.

**Table 1:** Joint measurement data collection

Measurement type	Baseline	Pre treatment	3 months	6 months	12 months	24 months
Active extension	x	x	x	x	x	x
Flexion	x		x	x	x	x
Passive extension	x	x	x	x	x	x

### 5.6.1 Recurrence

Recurrence at 6 months is defined as a change in extension deficit (measured as passive extension) of the reference joint of 6° or greater between 3 and 6 months post treatment. Recurrence at 12 months is defined as a change in extension deficit (measured as passive extension) of 20° or greater between 3 and 12 months post treatment [6]. This definition will be used to compare recurrence in each arm at 6 and 12 months post treatment.

### 5.6.2 Range of motion

Passive and active extension measurements and flexion measurements will be used to calculate the participant's passive and active RoM at baseline, and 3, 6, 12 and 24 months post treatment and will be used to assess how RoM changes over time.

### 5.7 Complications

Post treatment complications occurring since the previous follow up are recorded at 3, 6, 12 and 24 months post treatment. Details including date of onset, relatedness to study treatment and severity, are recorded as part of the usual trial adverse event reporting.

### 5.8 Further procedures

Data on further treatments and procedures received since the previous follow up will be collected at 3, 6, 12 and 24 months post treatment. This will include the timing of the treatments, whether or not the treatment is related to the reference hand/finger, and details of the treatment received.

### 5.9 Photographs in clinic

Three photographs of participants' hands will be collected at baseline and 3, 6, 12 and 24 months post treatment as follows

- A photograph of the reference hand in extension, taken directly above the hand (anterior view)
- A photograph of the reference hand in extension, taken from the side with the little finger closest to the camera
- A photograph of the reference hand in flexion, taken from the side with the little finger closest to the camera

These images will be used to obtain further measurements of active extension and flexion of the reference digit at each time point. The joint measurements obtained using these images will be used to validate and supplement goniometric measurements and will also be used for secondary analyses in the photography sub study.

## **5.10 Participant photographs**

Participants consenting to the photography sub study are shown how to take the required photographs (the same images as taken in clinic) of their hand at baseline and provided with detailed instructions. Sub study participants are asked to take standardised photographs of their study reference hand at baseline (as soon after the baseline visit as possible) and 3, 6, 12 and 24 months post treatment, which are then sent to the study team. Assessing the agreement between the goniometric measurements and measurements obtained using these images will be the primary goal of the photography sub study.

## **5.11 EQ-5D-5L**

The EQ-5D-5L is a validated instrument for assessing health related quality of life, comprised of 5 items, with 5 levels of response and a single general health status VAS [7]. Participants complete this questionnaire at baseline, 2 and 6 weeks post-treatment and 3, 6, 12 and 24 months post-treatment. Full details regarding the scoring and analysis of the EQ-5D-5L are given in the Health Economics Analysis plan.

## **5.12 Resource use**

Resource use data are collected in both participant and investigator CRFs at 3, 6, 12 and 24 months post treatment for the cost effectiveness analysis. Full details of the resource use data collected and the analysis of these data is given in the Health Economics analysis plan.

## **6. Other data collected**

Additional data relating to treatment preferences, comorbidity, concomitant medications, condition history and numerous other baseline characteristics are collected. A table summarising the data collection schedule is given in Appendix B.

### **6.1 Treatment preferences**

Participants are asked about their treatment preferences at baseline. Participants indicate whether they would prefer to receive collagenase, limited fasciectomy or have no preference. The baseline CRF is clear that their response to this question will have no impact on their chances of receiving a particular treatment. This data will be used as part of a subgroup analysis to explore possible treatment effect heterogeneity due to receipt (or otherwise) of the preferred treatment.

### **6.2 Demographic data**

Participants provide the following demographic details at baseline;

- Date of birth
- Sex
- Ethnicity
- Tobacco smoking status (Never, Current, Previous)
- Alcohol intake (Units per week)
- Which hand is their dominant hand

### **6.3 Condition history and diathesis indicators**

At baseline participants provide the following information regarding their history of symptoms and treatment of Dupuytren's disease and the presence of any diathesis indicators;

- Age at which they first experienced Dupuytren's contracture
- Presence of bilateral disease
- Receipt of past treatment with surgery and/or collagenase
- Family history of Dupuytren's contracture
- History of Garrod's pads and details of current symptoms if applicable
- History of Peyronie's disease if applicable
- History of Ledderhose disease and details of current symptoms if applicable

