The first set of regressions will be used to identify baseline characteristics associated with missing primary outcome data at any post treatment time point. The second will be used to identify baseline characteristics associated with missing primary outcome data at the primary endpoint (12 months) only. The third set will be used to identify baseline characteristics associated with withdrawal prior to treatment. Any baseline variables that are found to improve model fit (compared with the model with all parameters other than the intercept constrained to zero (not omitted)) in a likelihood ratio test of size 10%, will be added as fixed effects to the primary analysis model, and this model refitted. The results of this analysis will be reported in a similar manner to the reporting of the primary analysis (Appendix E-2).

We will also refit the primary analysis model using a multiply imputed dataset. A total of 250 imputations will be generated using multiple imputation by chained equations. The longitudinal structure of the data

will be accounted for by imputing the data in “wide” format. Further clustering by centre will be ignored for the purposes of the imputation model, (given that between centre heterogeneity is expected to be small and is not the focus of the analysis) but will be allowed for in the substantive analysis models fitted to each of the imputed datasets. Imputation will be carried out separately by randomised group to allow for possible interactions between randomised group and other variables included in the imputation model. Only patients that did not withdraw prior to treatment delivery will have their outcome data imputed, although patients that withdrew prior to treatment will be included in the imputation model. Patients who die during follow up will not have outcome data imputed following death. The variables that will be included in the imputation model are given in Table 3. Any baseline variables that are identified as being associated with missingness of post treatment PEM scores and/or non-receipt of treatment (see above) will also be included. Missing values in baseline variables included in the imputation model will be imputed as necessary (with any values imputed via single imputation methods for other analyses removed).

**Table 3:** Details of variables included in the imputation model

Variable	Type	Details	Univariate model (if imputation required)

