### 8.3.2 Other sensitivity analyses of the primary outcome

In addition to the sensitivity analyses investigating the possible influence of missing data, a further three sensitivity analyses will be conducted, investigating the possible influence of differential delay between baseline and treatment delivery in each arm, deviations from the scheduled timing of post-treatment follow ups and an analysis adjusting for additional predictors of disease recurrence. The results of these analyses will be reported in a similar manner to the reporting of the primary analysis (Appendix E-2).

Delay between baseline and treatment delivery differs between the two arms, with participants in the surgery arm generally waiting longer between the two time points. The additional delay in the surgery

arm may lead to greater disease progression by the point of treatment delivery. Hence the baseline measurements in the surgery arm may underestimate severity of disease (at treatment) in comparison to those in the collagenase arm, meaning covariate adjustment using the baseline measurements may lead to a treatment effect estimate which is biased toward zero. Thus the treatment effect estimate from the model adjusting for baseline (as in the primary analysis) may be anti-conservative (in the context of non-inferiority). We will therefore supplement this estimate, with an estimate from a model which adjusts for the PEM measurement taken at treatment delivery (in place of the baseline measurement with all other terms remaining the same as the primary analysis). Any missing treatment delivery PEM scores will be imputed with predicted scores via regression of the observed treatment delivery PEM scores on observed baseline PEM scores and reference joint (MCP or PIP). If the baseline PEM score is also missing then the reference joint strata specific means will be used instead.

To investigate the robustness of the primary analysis to deviations from the scheduled timing of study visits/assessments, the primary analysis models will be refitted using only participants who had PEM scores collected within +/-14 days of the scheduled visit date at 3 and 6 months and within +/-91 days of the scheduled visit date at 12 and 24 months. Any missing baseline PEM scores will be imputed as for the primary analysis.

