We will investigate whether the inclusion of additional baseline predictors of recurrence has any impact on the results of the primary analysis. The primary analysis model will be refitted including four additional predictors of recurrence collected at baseline; presence/history of bilateral disease (binary), presence/history of Garrods pads, Peyronie's disease or Ledderhose disease (binary), family history (binary) and age at which the patient first experienced Dupuytren's contracture (linear term). This analysis will be based on complete cases only.

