#### **8.4.7 Recurrence**

Recurrence will be defined in a binary manner (recurred or not recurred) at 6, 12 and 24 months post-treatment. Recurrence at the 6 month follow up is defined as an increase in passive extension deficit of the reference joint of 6° since the 3 month post treatment follow up. Recurrence at 12 and 24 months is defined as an increase in passive extension deficit of the reference joint of 20° since the 3 month post treatment follow up. These binary outcomes will be modelled using mixed effect logistic regression models adjusting for study reference joint (MCP or PIP), study reference digit, baseline PEM score and baseline passive extension measurement as fixed effects with centre as a random effect. These models will include all participants for whom the relevant (i.e. month 6 or month 12) binary indicator of recurrence can be derived using the available data. If perfect prediction occurs due to empty strata at some covariate combinations, then participants with study reference digit indicated as middle, index or thumb will be pooled so that reference digit becomes a three category covariate (little, ring, other). If the issue persists, then the term for study reference digit will be dropped from the model. If the baseline PEM score and/or baseline passive extension measurement is missing, then they will be imputed using predicted values via regression of the observed values on observed baseline MHQ scores and reference joint (MCP or PIP). If the MHQ score is also missing, then missing baseline PEM scores and/or baseline passive extension measurements will be imputed using predicted values via regression of the observed values on the observed baseline URAM scores and reference joint. If baseline URAM score is also missing then missing baseline PEM scores and/or baseline passive extension measurements will be imputed with the reference joint strata specific means. For both analyses, the estimated odds ratios for allocation (and two-sided 95% CIs) will be reported. This model will also be used to derive the absolute differences in risk of recurrence (together with two-sided 95% CIs) at representative values of the covariates (mean of the continuous covariates, both levels of reference joint, two levels of reference digit (ring or little) and marginalising over the centre random effects). We will also test composite null hypotheses about the absolute difference in incidence of recurrence at 12

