and 24 months post-treatment. Specifically we will report one-sided p-values from four Wald tests of  $H_0: d \geq 10\%$  , where  $p < 0.025$  indicates statistical significance, and  $d = \Pr(\text{Recurrence} \mid \text{Collagenase}, X) - \Pr(\text{Recurrence} \mid \text{Surgery}, X)$  for the four covariate patterns  $X$  outlined above (MCP + Ring, MCP + Little, PIP + Ring, PIP + Little).

Due to the Coronavirus pandemic, a substantial proportion of participants were followed up remotely at 3, 6, 12 and 24 months post-treatment, and did not have goniometric measurements taken. Missingness due to remote follow up, as well as attrition, mean a substantial proportion of the post-treatment goniometric measurement data will be missing. The proportion of missing data at each time point will be summarised by randomised group, as will the available reasons this missing data. The principal analyses of recurrence outlined above (based on the available goniometric measurements) will be repeated using two alternative analysis sets. The first analysis set will supplement the available goniometric measurements with measurements obtained using photographs taken by clinical investigators. If photographs taken by the clinical investigators are not available, then measurements obtained using photographs taken by the participant will be used (note this would include photographs submitted by participants in the photography sub-study, as well as photographs submitted by non-sub-study participants who could not attend clinic visits due to the pandemic). The second analysis will use the multiply imputed dataset(s) generated as part of the analyses specified in Section 8.3.1. Both analysis sets will be analysed using the same models used for the analysis of the available goniometric measurements, with estimates and tests being reported analogously.

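### The four baseline factors that the SAP calls predictors of recurrence enter only a PEM sensitivity analysis, not the recurrence analyses or the imputation reused for them

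*SAP*

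**What the plan says.** Section 6.3 records the condition history and "the presence of any diathesis indicators" at baseline, so the data will exist for trial participants in general.

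Section 8.3.2 announces "an analysis adjusting for additional predictors of disease recurrence" and then specifies it: "The primary analysis model will be refitted including four additional predictors of recurrence collected at baseline". The four terms are bilateral disease, one composite of Garrod's pads, Peyronie's or Ledderhose disease, family history, and age at first contracture. The outcome is the PEM score, and "This analysis will be based on complete cases only".

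Section 8.4.7 fits a logistic model to recurrence. Its covariates are set by the phrase "adjusting for study reference joint (MCP or PIP), study reference digit, baseline PEM score and baseline passive extension measurement as fixed effects"; a random intercept allows for differences between centres. Two repeat analyses use the same models. One fills gaps in goniometry from photographs. For the other, "The second analysis will use the multiply imputed dataset(s) generated as part of the analyses specified in Section 8.3.1".

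Those datasets come from the imputation model in Table 3 of Section 8.3.1, which lists none of the four factors. Other variables are admitted by one rule: "Any baseline variables that are identified as being associated with missingness of post treatment PEM scores and/or non-receipt of treatment".

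**The concern.** The SAP gives these factors a role defined by recurrence and then applies them to a different outcome. Section 8 makes maintenance of correction one of the key secondary objectives and attaches a 10% non-inferiority margin to recurrence at 12 months. Section 8.4.7 also expects much of the post-treatment goniometry to be missing, because of remote follow-up in the pandemic as well as attrition.

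In that setting, known predictors of the outcome matter most for the missing-data assumption. The available-case analysis is valid if, given arm and the model covariates, being evaluable is unrelated to recurrence. The imputed analysis makes the corresponding assumption given the Table 3 variables. If a diathesis factor predicts recurrence beyond those variables, and also relates to who attends for measurement, the assumption fails for a reason that the collected data could have dealt with. The departures from missing at random explored in Section 8.3.1 cover PEM only, so no planned analysis would show the effect on recurrence.

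**Working it through.** **1. The plan's own figure.** The only sample size stated is for PEM (Section 3: margin 6, SD 22, one-sided 2.5%, 90% power). The normal approximation gives n = 2 × 22² × (1.960 + 1.282)² / 6² = 282.5, so 283 per arm. The exact t-test has power 0.8995 at 283 and 0.9005 at 284. Hence 284 per arm, 568 in all, and 568 / 0.8 = 710. The figure reproduces. The SAP gives no recurrence rate, power or sample size for the recurrence test.

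**2. Where the four terms appear.**

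| Place in the SAP | Variables | Any of the four? |
|---|---|---|
| 8.3.2, PEM sensitivity refit | primary model plus the four | Yes, all four |
| 8.4.7, principal recurrence model | arm, joint, digit, baseline PEM, baseline passive extension, centre | No |
| 8.4.7, photograph-supplemented and imputed sets | same models | No |
| 8.3.1, Table 3 | PEM, URAM, MHQ, serial joint measurements, joint, crossover, complications, further treatment | No |
| 8.3.1, candidates for addition to Table 3 | age, sex, smoking, alcohol, previous treatment, comorbidities, number of digits, MHQ, URAM, EQ-5D VAS | No |

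The last row closes the data-driven route twice. The four factors are not candidates. The screening also looks at missing PEM or withdrawal before treatment, not at missing goniometry. Current age is screened; age at first contracture is not.

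**3. Cost with complete data.** All inputs in this step are assumptions except the 284 per arm, the margin and the test level. Four independent binary factors with prevalences 40%, 20%, 30% and 50% stand in for the four terms, each with the same odds ratio. The 10% test was simulated 1,000 times per scenario, using a logistic model, a standardised risk difference d and a one-sided Wald test at 2.5%.

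| Control risk | Odds ratio per factor | Power at d = 0, without → with | Rejection at d = 10%, without → with |
|---|---|---|---|
| 10% | 1.5 | 0.974 → 0.977 | 2.2% → 2.5% |
| 10% | 2.0 | 0.973 → 0.978 | 1.8% → 2.4% |
| 20% | 1.5 | 0.849 → 0.853 | 2.8% → 2.7% |
| 20% | 2.0 | 0.843 → 0.864 | 1.9% → 1.8% |
| 30% | 1.5 | 0.707 → 0.728 | 1.8% → 1.7% |
| 30% | 2.0 | 0.725 → 0.772 | 2.5% → 2.2% |

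The Monte Carlo standard error of a 2.5% rejection rate is √(0.025 × 0.975 / 1000) = 0.5 points, so no row shows inflation. The power difference runs from 0.3 points (0.977 − 0.974) to 4.7 points (0.772 − 0.725). In the last row the mean standard error of d falls from 3.84 to 3.68 points, or 4%.

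**4. With missing goniometry.** The SAP gives no prevalences, effects, recurrence rates or attendance pattern by arm, so a bias can be computed only from invented inputs. What can be said is qualitative: the omission leaves open a dependence between being evaluable and recurring that the four variables might have reduced.

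**The case against.** The strongest reply is that choosing covariates is the sponsor's decision. Section 8.4.7 already adjusts for joint, digit, baseline contracture and baseline PEM, and nothing in the SAP promises diathesis adjustment of recurrence. The imputation is run separately by arm. It conditions on serial passive extension, active extension and flexion, and on further treatment, all of which lie closer to recurrence than baseline history does. Photographs fill some gaps as well. Remote follow-up in the pandemic was largely administrative, so it need not depend on diathesis. Using the four terms in a PEM analysis is also not misplaced, because recurrence may affect hand function. All of this stands. It limits the likely harm but does not explain why predictors named for recurrence are absent from every recurrence analysis.

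A reader might infer three stronger things.

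- *That chance imbalance in these factors biases d.* It does not; it is part of the sampling error already in the confidence interval. With 150 evaluable per arm (assumed) and risks of 10% or 20%, the SE of d at the margin is √((0.09 + 0.16)/150) = 4.1 or √((0.16 + 0.21)/150) = 5.0 points. On assumed factor effects, imbalance contributes an SD of 0.6 to 1.5 points, about 2% to 9% of that variance.
- *That the one-sided error rises well above 2.5%.* If attendance is assumed to depend on the factors in one arm only, or in opposite ways in the two arms, a crude d can be biased by −0.6 to −3.1 points, with an error of 3.4% to 9.2%. Mirror-image assumptions give about 0.5% to 1.9%. If both arms lose participants alike and true risks are equal, the bias is zero. The SAP supports none of these patterns over the others. A crude d also does not describe the imputed analysis.
- *That the recurrence test ignores prognostic factors.* It leaves out these four and adjusts for others.

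**Conclusion.** The point holds as a cheap improvement to the plan; it does not invalidate the recurrence test. That the four factors are omitted follows from the text alone. With complete randomised data the cost is modest precision: about 0.3 to 5 points of power, on assumed risks of 10% to 30%, odds ratios of 1.5 to 2 and 284 evaluable per arm, with no inflation of the 2.5% error.

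The weightier part is the imputation. It was built for PEM and is reused for recurrence, range of movement, active extension and flexion. Leaving out variables that the SAP itself ties to recurrence makes the missing-at-random assumption weaker than it need be. The direction and size of any resulting bias are unknown, and the existing Table 3 variables may already absorb part of the factors' effect.

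**What to change.** 1. **Imputation (Section 8.3.1, Table 3).** Add the four terms as already defined in Section 8.3.2, and impute their own missing values there. The imputed analyses in Sections 8.4.7 to 8.4.10 then condition on them. Counting each time point, Table 3 already lists 36 variables; this makes 40.

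2. **Recurrence (Section 8.4.7).** Add one sensitivity model at 12 months and one at 24 months that include the four terms. Report d with its 95% CI for the same four joint-by-digit patterns, averaged over the observed distribution of the diathesis terms, so that d stays defined once they are in the model. Show it beside the principal result, which does not change.

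3. **Fallback.** If a sensitivity model separates or does not converge, keep the terms in the imputation only and say so.

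The cost is SAP wording and a little more analysis; the data are already collected. The drawback is four more parameters with limited events. At 10% risk and 150 evaluable per arm (assumed) there would be about 2 × 150 × 0.10 = 30 events, against up to eight fixed-effect slopes now (arm, joint, four for digit, PEM, passive extension) and twelve with the additions. That is why the model should be a sensitivity analysis and not replace the principal one.
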